IIR03-315 Effectiveness and Implementation of Brief Cognitive Behavioral Therapy in
CBOCs

Funding Agency: Office of Research and Development

Principal Investigator: [name]

January 26, 2018

Abstract

Provide a summary of the study (recommended length: less than 500 words).

Depression is a serious health condition that places tremendous burden on patients and healthcare systems and is especially prevalent among Veterans. The delivery of complex evidence-based psychotherapy depression care is challenging, especially in settings such as primary care and community-based clinics. Within the Veterans Health Administration (VHA), efforts are needed to assist community-based outpatient clinic (CBOC) clinicians to deliver evidence-based psychotherapy for depression. The proposed 4-year multi-site trial seeks to train and assist (facilitate) CBOC clinicians in the use of a brief cognitive behavioral therapy (bCBT) and to subsequently monitor the effectiveness of this treatment on Veteran outcomes using a direct-referral versus enhanced usual care patient randomized trial design. Aim 1 will develop a series of strategies to train and assist CBOC clinicians in the use of bCBT at 16 CBOC sites connected to the Houston and Oklahoma City VA Medical Centers. Initial development of these strategies will involve CBOC clinician feedback in an iterative fashion that refines and enhances the training and support offered. Collectively, the development and assessment of these strategies will occur through a formal “formative evaluation” process. Formative evaluation will include a needs assessment as well as modifications to the clinical (bCBT) and implementation (clinician training and support) approaches. Following Aim 1, Aim 2 will seek to determine whether depression outcomes for Veterans differ as a function of the intervention (direct referral to bCBT provided by CBOC clinicians vs. enhanced usual care) at post-treatment (4-month), and 8- and 12-month follow-up. A total of 232 Veterans with clinically elevated symptoms of depression will be recruited from CBOC clinics associated with the Houston and Oklahoma City VA medical centers (8 CBOCs per station). Eligible Veterans will be randomized to either 1) a direct referral to a CBOC bCBT trained VA provider or 2) an Enhanced Usual Care (EUC) arm where participants will receive depression information and a depression tool kit as well as a note placed in their electronic medical record. EUC participants will be asked to talk to their primary care provider about additional depression treatment options. No participants in either the bCBT or EUC groups will be restricted in any way from the receipt of VHA services. Rather, the study will use VHA databases and chart review procedures to document and control for health care use during the study period.

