Quality of Life and Functional Status: Quality of life will be assessed using the 12-Item Short Form Health Survey for Veterans (SF-12V),⁴⁷ an instrument adopted by VHA as a performance measure of functional status. The SF-12V is comprised of 12 items from the SF-36. The SF-12 consists of two scores, physical (PCS) and mental (MCS) functioning. Covariates: Demographic data will include age, gender, ethnicity, income, marital status, education, employment, and distance from the VA and/or CBOC. Diagnoses of Anxiety and Depressive Disorders will be assessed using the MINI depression and anxiety modules. Coding of these variables will be dichotomized for each type of depressive and anxiety disorder assessed. PTSD will be assessed using the PTSD Checklist- Civilian Version (PCL-5), a standardized self-report rating scale that corresponds to *DSM-IV* symptoms of PTSD and possess strong psychometric properties.^{50,51} Comorbid Medical Conditions/Medical Complexity will be calculated using the Charlson Comorbidity Index (CCI) as defined by VA database extractions for the 12 months prior to the baseline date. The Charlson score has been widely used in the literature for assessing morbidity and mortality in a wide range of patients.⁵² The ICD-9 codes constituting each condition will be based on those identified in Deyo’s adaptation.⁵³ Co-existent Use of Psychotropic Medications will be collected to control for possible effects of ongoing pharmacologic treatment. VA databases and participant surveys will be used to assess for the presence of mental health medications. The study team has experience evaluating the impact of psychotropic medications in psychotherapy trials and has also conducted several VA database studies looking at the impact of antidepressant medications on depression care quality.^{8,54} [name] (psychiatrist and Co-I) will lead efforts related to psychotropic medication tracking which will include information on start date of medication, dose, and days’ supply. Medication use will be coded for presence or absence, changes to type or dosage, as well as medication possession ratios (days of medication relative to time frame of medication

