Quantitative analyses will use descriptive data related to clinician adoption, fidelity ratings, and bCBT utilization (participant engagement, treatment completion, and total session exposure). Data will be compared to our prior work to explore if differences exist between VA hospitals (HOU and OKC) and the CBOCs engaged in the current proposal. We will also use VA databases to explore the use of psychotherapy services pre- and post- implementation using depression ICD-9 and psychotherapy CPT codes as used by the PI in prior work.^{15,59} Qualitative data for aim 2 will use a combined inductive and deductive analytic approach given our desire to understand the firsthand accounts of stakeholders (inductive) while incorporating a priori codes using elements from our implementation frameworks (deductive). The analytic approach will examine interview and field-note data from patients, providers, clinic leaders, and leadership. This entails examining the textual data from the insider's perspective to uncover patterns in the experiences under investigation.^{43, 60-62} The result is the description of a deeper structure, a synthesis of the data into one explanatory framework.⁶² Field notes and transcripts will be read and re-read, and key terms coded. Initial coding will identify significant statements, sentences, or quotes that provide an understanding of how the participants experienced/used bCBT. Study coders will develop clusters of meaning or themes to produce a written description of the contextual elements. Coding will culminate in a codebook that includes a narrative of the central

themes with illustrative quotes, along with a visual portrayal of the data including the factors and outcomes related to the central phenomenon.

The above listed coding methods will be used during the progress-focused formative evaluation. A briefer coding method will be used during other formative evaluation phases. These less rigorous coding strategies, informed by [name] et al, fit well with the focused aims of the formative evaluation phases and are seen as critical to ensure project feasibility. Coding will be conducted by a qualitative investigator at the Houston HSR&D CoE ([name]). [name], a medical anthropologist, will lead the qualitative inquiry. She will collaborate with [name] (senior consultant and co-I) and coordinate coding procedures with the study team.

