Collection of safety information will commence when the first participant is enrolled in the study; this is anticipated to occur during March 2015. Safety information may be collected either 1) during baseline and follow up assessments, 2) during bCBT sessions, or 3) during telephone contacts with participants made for purposes of scheduling assessments and/or treatment sessions. All participants will complete comprehensive assessments via telephone at baseline and at 4-, 8-, and 12-month follow-ups. Symptoms of depression and suicidal ideation will be assessed at these time points. Secondly, those participants assigned to the bCBT group will complete measures of depression during each session with their study clinician; these sessions will occur either in person or over the telephone depending on patient preference. Third, the Research Coordinator or RA will periodically contact patients to schedule study-related appointments. The participants or other informants may report information related to their safety at those times.

Conditions that would trigger an immediate suspension of the research:

This intervention will compare a brief, structured cognitive-behavioral intervention with usual care practices in VA CBOCs. The active treatment, bCBT, utilizes well-established psychotherapeutic techniques to enhance patients' self-management of mood and physical functioning. No medications, invasive procedures, or untested techniques will be used. As such, this protocol is judged to be of low risk. We do not anticipate the occurrence of events that would necessitate the immediate suspension of research because of 1) the low probability of adverse events from the intervention in either arm of the study, 2) all participants will continue to receive usual care services within the VA, and 3) treatment for depression will not be withheld from any participants.

Specify procedures to determine when and how to notify individual participants or their health care providers of findings that may affect the participant's health or welfare:

The decision to contact a patient and/or their health care provider regarding patient welfare can be made in two ways. First, the Project Coordinator, RA, or independent evaluators will conduct routine checks on participants' safety and well-being, including an assessment of suicidal ideation, during baseline and follow up assessments. These study personnel will notify the patient and/or their healthcare provider as necessary.

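### The Aim 1 pre/post comparison and the Charlson score name only ICD-9 diagnosis codes, although enrolment runs from March 2015; any encounters coded in ICD-10 would be missed

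*Combined protocol and SAP*

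**What the plan says.** Two derivations from VA databases depend on diagnosis codes.

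- **Psychotherapy use before and after implementation** (section 5.6, Aim 1 analyses). The team will "explore the use of psychotherapy services pre- and post- implementation using depression ICD-9 and psychotherapy CPT codes", in the manner of earlier work by the investigator. CPT identifies the service; ICD-9 identifies the depression diagnosis.
- **Charlson index** (section 5.5, covariates). The index is computed "as defined by VA database extractions for the 12 months prior to the baseline date". On the code set, the text says "The ICD-9 codes constituting each condition will be based on those identified in" a published adaptation of the index.

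On timing, section 6.0 says of the first enrolment that "this is anticipated to occur during March 2015". The Abstract describes a 4-year project, and the document is dated "January 26, 2018". ICD-10, a crosswalk and code lists that depend on calendar date appear nowhere in the protocol.

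The Aim 2 models (section 5.6) list antidepressant use, outpatient mental health care, treatment modality and site as covariates. Charlson is not among them.

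**The concern.** A derivation that accepts only ICD-9 diagnoses finds nothing in an encounter recorded in ICD-10. If the coding system changed during the data window, the change would fall within or near the period that the pre/post comparison is meant to assess. A coding artefact could then be mixed with any real effect of implementation on psychotherapy use, and this is the only database comparison of that use over time that the plan describes.

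For the Charlson score, the loss would follow enrolment date. Early enrollees would be scored on a complete look-back and late enrollees on part of one or none. That would distort the baseline description of comorbidity. It would also distort any later use of the score as a patient characteristic.

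The text names ICD-9 as the rule, so this is more than an unstated detail. An analyst who noticed the problem would have to depart from the plan without a pre-specified replacement.

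**Working it through.** The plan prints no figure on this point, so there is none to reproduce. The check is a timeline calculation.

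**Inputs from the documents:** ICD-9 diagnosis codes for both derivations (sections 5.5 and 5.6); 12-month look-back (section 5.5); first enrolment March 2015, taken as 1 March (section 6.0).

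**Assumptions, not in the documents:** diagnoses are recorded in ICD-10 from *s* months after 1 March 2015. A switch on 1 October 2015 is *s* = 7; *s* is varied from 0 to 36. Accrual is even over *R* = 18 to 36 months.

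**Charlson look-back.** For a baseline at month *b*, the share of the look-back lying after the switch is min(12, max(0, *b* − *s*))/12. Averaging over *b* from 0 to *R* gives:

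- 0, if *R* ≤ *s*
- (*R* − *s*)²/(24*R*), if *s* < *R* ≤ *s* + 12
- (*R* − *s* − 6)/*R*, if *R* > *s* + 12

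For *s* = 7: *R* = 18 gives 11²/(24 × 18) = 121/432 = 28%, and *R* = 36 gives (36 − 7 − 6)/36 = 23/36 = 64%.

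Mean share of look-back time affected:

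| Switch month *s* | *R* = 18 | *R* = 24 | *R* = 30 | *R* = 36 |
|---|---|---|---|---|
| 0 | 67% | 75% | 80% | 83% |
| 7 | 28% | 46% | 57% | 64% |
| 12 | 8% | 25% | 40% | 50% |
| 24 | 0% | 0% | 5% | 17% |
| 36 | 0% | 0% | 0% | 0% |

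At *s* = 7, the share of enrollees with any look-back time after the switch is (*R* − 7)/*R*: 61%, 71%, 77% and 81% for the four accrual lengths. The share whose whole look-back lies after it is max(0, *R* − 19)/*R*: 0%, 21%, 37% and 47%.

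**From time to score.** A chronic condition coded once in the ICD-9 part of the look-back still counts, so the affected time is not the fraction of the score lost. Missing codes can only remove conditions, so each score is either too low or unchanged. Only enrollees whose whole look-back is in ICD-10 must score 0.

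**Pre/post psychotherapy use.** Section 5.6 does not say whether use is a count or a proportion, and the plan gives no dates for the two periods.

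- *Count of visits, each needing a depression code.* With constant true use and a post period of *L* months starting at first enrolment, the share captured is *s*/*L* when *s* < *L*. At *s* = 7 this is 7/12 = 58%, 7/24 = 29% and 7/36 = 19%, which would look like falls of 42%, 71% and 81%. At *s* = 36 nothing is lost for any of these periods.
- *Proportion of diagnosed patients who receive psychotherapy.* Patients first diagnosed after the switch leave both numerator and denominator. If those who remain use psychotherapy at the same rate, the proportion need not change; if they differ, it can move either way. The post-period cohort shrinks and the direction is undetermined.

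**The case against.** The strongest reply is that the decisive fact is missing from the documents: they do not say when, or whether, VA coding moved to ICD-10. That stands. The conclusion must be conditional, and the table shows that the affected look-back time ranges from none to most of it. A reader might infer from the March 2015 start that later encounters are certainly missed; the documents do not establish that.

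Three other stronger readings also fail.

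- *Psychotherapy use rests on ICD-9 only.* It does not. CPT codes identify the service, and ICD-9 selects the depression diagnosis.
- *Use would appear to collapse after implementation.* The 42% to 81% falls need a count of visits that each carry a depression code, together with the assumed dates. The Aim 1 sentence points to prior work, and section 2.0, under one of the same citation numbers, reports a proportion: 22% of urban and 15% of rural Veterans with at least one session in the year after a depression diagnosis. For such a measure the direction is open.
- *Charlson scores fall by the share of look-back affected.* As shown, that share is time, not score.

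It can also be said that little depends on this. The pre/post work is exploratory within a descriptive aim, and the response-prediction analysis (section 5.6, other analyses) does not name Charlson among its examples of predictors, although its clinical characteristics could include it. That stands and limits the consequence. Finally, a sudden absence of diagnoses would probably be noticed. That is likely, but noticing it does not supply a pre-specified remedy.

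**Conclusion.** The point holds in conditional form. For data from 2015 onward the plan names ICD-9 as its only diagnosis code set in two derivations. If encounters in the window are coded in ICD-10, later depression diagnoses and comorbidities would be missed.

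The effect on psychotherapy use is downward for visit counts and undetermined for a proportion of diagnosed patients. The effect on the Charlson score is downward or nil. The size depends on an unprinted switch date. On even accrual over 18 to 36 months, the mean look-back time affected is 67–83% for a switch at month 0, 28–64% at month 7 (the 1 October 2015 assumption), 8–50% at month 12, 0–17% at month 24 and none at month 36.

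The consequence is confined to the exploratory Aim 1 comparison and the baseline comorbidity score. A reader might infer a bias in the Aim 2 arm contrast. The documents do not support that: Charlson is not in those models, and with randomisation any under-scoring should fall on both arms alike. The change is still worth making, because the written rule is specific and correcting it costs little.

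**What to change.** In the Aim 1 analyses of section 5.6, define depression diagnoses by an ICD-9-CM list for encounters before the coding change and an equivalent ICD-10-CM list for encounters after it, assigned by encounter date. Keep the psychotherapy CPT list. Plot monthly counts and check for a step at the change date before interpreting any pre/post difference.

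In the covariates part of section 5.5, define the same Charlson conditions by matching ICD-9-CM and ICD-10-CM lists, each applied by encounter date within the 12-month look-back.

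The cost is a short addition to each of two paragraphs, a second code list in the extraction program and one simple check. No new data, participants or staff are needed. The small downside is that the two code sets may not map perfectly; any residual step should be reported.

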The bCBT intervention will be delivered by VA CBOC clinicians at the Houston and Oklahoma City affiliated CBOCs. All mental health clinicians at the 16 CBOC sites will be approached for inclusion in the study. We anticipate that a minimum of 12 clinicians will be enrolled, with a realistic estimate to approach 15 or more enrolled clinicians before the end of the trial, given staff turnover and program expansion efforts. Clinicians will receive online bCBT training with an emphasis on care for Veterans in the CBOC setting. Clinicians will be invited to participate by referral from clinic directors and/or VISN 16 mental health leadership. The study team will follow-up with the clinician and his/her supervisor to verify that study participation is appropriate. CBOC clinicians will receive advocacy (when needed) from the study staff and VISN leadership (see Appendix 2, letters of support) to resolve barriers to participation. Clinicians will not be restricted based on discipline or prior CBT experiences, but will be expected to have an interest in obtaining training and willingness to use bCBT in their practice. As seen in our ongoing trial, we anticipate that nurses, social workers, psychologists, counselors, and physician assistants will participate. The study team will try to work with clinicians to receive workload credit, but will not guarantee.

All enrolled clinicians will receive a series of training and facilitation tools to assist their use of bCBT in their VA care settings. The proposed implementation strategy (training and facilitation tools) will be based on our prior work as outlined by Mignogna, et al. 2014.²² The proposed implementation strategy will initially include a series of techniques but will be modified with input from CBOC stakeholders during the development and refinement process. The initial strategy will include the following facets:

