Following randomization, EUC participants will receive feedback and educational materials about managing depression³⁷ and a letter encouraging them to discuss treatment options with their VA primary care provider (see Appendix 9, Patient Educational Brochure and Appendix 11, Usual Care Letter). The EUC arm represents a modest enhancement to the ongoing CBOC practices in that it will add routine, comprehensive screenings for all consenting patients, identification of depressive symptoms, encouragement to address depression using print-based materials, and notification of the patient's primary care provider. EUC participants will be given the same reimbursement as bCBT participants and will be asked to complete the same assessments at 4-, 8-, and 12-month follow-ups. Following each assessment, findings will be documented within each patient's electronic medical record. Because depression identification and treatment are a priority within VA, we fully expect that enrolled participants may receive depression treatment (e.g., antidepressants or depression care management). Although medications are a first line of care for depression, data suggest that antidepressant medication use remains modest.³⁸

NOTE: Participants in EUC will NOT be restricted from any mental health services. To address the possible confounding effects of co-occurring mental health treatments, we will measure health services utilized, with particular emphasis on use of psychotropic medications, psychotherapy, and other specialty mental health care.

Minimization of Risk

Provider Participants: Prior to any provider recruitment efforts, union representatives at the Houston and Oklahoma City VAMCs will be notified of the study proposal. Potential therapists will be referred by their clinic director and/or VISN mental health leadership and subsequently screened for appropriateness by the study investigators. The study team will be careful to ensure that VISN leadership or clinic directors do not require clinicians to engage in this work. Any clinician who does not wish to participate will be excluded. Clinician participants final decision to participate or not will not be made known to their supervisor or VISN leadership. Clinicians who wish to participate (receive the training and provide care) will be enrolled. Therapist information related to performance and feedback will be coded within the study so that no therapist specific information will be identifiable outside of the study itself.

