5.3 Informed Consent Procedures

The consent process will occur before administration of the baseline assessment for Veterans and before training for clinicians. LAC members will be consented during the first month of the active phase of the project. The informed consent process will be completed by the local Site RA or the Project Coordinator. This study does not involve subjects with impaired decision-making ability or who have legally authorized representatives.

Clinician Participants

Clinicians will be recruited from all 16 CBOCs and included as study participants. Local union representatives will be informed of the study. Currently, there are 24 mental health clinicians who provide care to the 16 identified CBOCs.

The study is requesting a waiver of documentation of informed consent for clinician participants. Potential therapists will be referred by their clinic director and/or VISN mental health leadership and subsequently screened for appropriateness by the study investigators. Clinicians identified as interested will be contacted via email by study staff to confirm interest. A follow up call will be made if there is no email response from the clinician. When interest is confirmed, a time will be set up to review the informational document (see Appendix 4E) with the clinician by phone. The informational document will be emailed to clinicians prior to the meeting. During the meeting, the study team member will review the document and explain all procedures requested of a participating clinician and address any questions posed. In some instances, the consent process will take place during the initial phone call confirming interest if the clinician is available at that time. If so, a copy of the informational document will be emailed at that time. Once a clinician gives their consent, their name will be added to the master list of enrolled participants.

Veteran Participants

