5.6 Data Analysis

Sample Size and Power Calculations:

Provider Sample (Implementation Data; Aim 1)

No formal sample size calculations were used for the implementation-focused elements of this project. Rather, the team will invite all CBOC providers at all sites within the HOU and OKC VAMCs to participate and subsequently evaluate how many providers opted to engage in the bCBT project. These procedures are common for implementation-focused trials that often have a smaller pool of “subjects”. Designs of this nature often look less at statistical significance and

instead focus more on descriptive quantitative data and depth interviewing and qualitative analyses to determine impact and “lessons learned”.

Veteran Sample (Effectiveness Data; Aim 2)

Sample-size calculations indicate that 232 patients will need to be randomized to address the primary hypothesis for aim 2. Based upon our current project, we will need to recruit 300 Veterans. Approximately 30% of recruited participants were screened ineligible due to subthreshold anxiety and/or depression scores.

We will use unequal randomization to reduce unnecessary recruitment, resulting in 138 patients for bCBT and 94 for EUC. In determining the sample size, we first determined the number of participants needed to have 80% power to detect significant differences in the primary outcomes between our groups. We then inflated this to account for intraclass correlations among patients and for attrition and loss to follow-up. A sample size of 70 patients in both the bCBT and EUC groups (140 total) is needed to detect a difference in the means of the primary outcome that reflects a small effect size of .30, using a 2-sided *t*-test with 80% power at the .05 significance level, adjusted for repeated measures.⁵⁶ The small effect size was chosen to ensure an adequate sample size to address multiple study aims and outcomes. The bCBT sample size was then inflated by $[1 + (m - 1) c]$ to account for the intraclass correlation due to clustering of patients within bCBT clinicians.⁵⁷ Based on the sample size of 70 bCBT patients, an average of 5.8 patients per therapist, and an assumed correlation, *c*, among patients of .10,⁵⁷ our inflation factor is 1.48 ($70 \times 1.48 = 104$). A clustering inflation factor was not used for the EUC group. Both the bCBT and EUC groups are inflated to account for attrition rate at 12 months of 25%.

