Aim 2 will determine whether depression and quality of life outcomes differ as a function of the intervention at posttreatment, and at 8- and 12-month follow-ups. All analyses will be done on an intention-to-treat basis. Following the recommendation of the CONSORT group, we will not test for differences in baseline characteristics or adjust subsequent analyses for any variables we did not decide a priori to include in the regression models.⁶³ To compare changes between the 2 groups over time, we will use a longitudinal, mixed-model analysis containing terms for the intercept, treatment, time period and interaction between time and treatment. Separate models will be run for each outcome (PHQ-9, BDI, SF-12 PCS and MCS) and for the combined outcome of whether or not the patient responded to treatment as measured by both a 50% reduction in PHQ-9 and BDI-II. Linear regression will be run for the continuous outcomes and logistic regression will be used for the combined depression outcome. We will include the use of antidepressant medications, receipt of outpatient mental health care, the modality of treatment (e.g., telephone, in-person, combination), and the stratification variable, site, in the analyses to control for any possible differences that might exist between the treatment arms that might impact our outcomes. The interaction between time and treatment will indicate whether there is a difference over time between the 2 groups. We will conduct sensitivity analyses to evaluate whether the reasons for loss to follow-up at the various time periods are related to the observed values of the outcome variable, using tests for missing completely at random and tests for nonrandom missingness.⁵⁶

Analyses for Aim 2 will occur exclusively at the Houston HSR&D CoE under the direction of the PI ([name]), study statistician (Co-I [name]), and study data analyst ([name]).

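### The sample size allows for patients clustering within bCBT clinicians, but the Aim 2 model names no clinician effect; a nominal 5% per-visit comparison then runs at about 7.3% on the plan's own inputs

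*Combined protocol and SAP*

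**What the plan says.** The Veteran sample-size text in Section 5.6 enlarges the bCBT arm "to account for the intraclass correlation due to clustering of patients within bCBT clinicians". The inputs are a correlation of 0.10 and this cluster size: "Based on the sample size of 70 bCBT patients, an average of 5.8 patients per therapist". They give a factor of 1.48, so 70 becomes 104. For the other arm it states: "A clustering inflation factor was not used for the EUC group". Both arms are then raised for 25% attrition, giving 138 and 94.

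The Aim 2 analysis text, also in Section 5.6, says "we will use a longitudinal, mixed-model analysis containing terms for the intercept, treatment, time period and interaction between time and treatment". It adds antidepressant use, outpatient mental health care, treatment modality and site. On the test, it says: "The interaction between time and treatment will indicate whether there is a difference over time between the 2 groups". It gives no random-effects structure and does not say whether baseline is one of the time periods. Clinician factors appear only in the exploratory prediction of response within bCBT.

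On clinician numbers, Section 5.1 says "We anticipate that a minimum of 12 clinicians will be enrolled" and realistically expects 15 or more. Section 5.3 says: "Currently, there are 24 mental health clinicians who provide care to the 16 identified CBOCs".

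**The concern.** The plan treats clinician clustering as real, and as specific to one arm, when it sets the sample size. It does not carry this into the inference. With a clinician effect in the bCBT arm, that arm's mean is more variable than independent patients would make it. A model without the effect reports standard errors that are too small, confidence intervals that are too narrow and p-values that are too low. This applies to PHQ-9, BDI-II, the two SF-12 scores and the response outcome. Extra patients are recruited to pay for clustering that the stated analysis then ignores.

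Site does not replace a clinician effect. A site term common to both arms cannot absorb variation that acts in bCBT alone, and that variation stays in the treatment contrast.

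**Working it through.** **Reproducing the plan's figure.** Design effect = 1 + (m − 1) × ICC = 1 + 4.8 × 0.10 = 1.48. Then 70 × 1.48 = 103.6, or 104. With attrition, 103.6 / 0.75 = 138.1 and 70 / 0.75 = 93.3, which give the stated 138, 94 and 232. The 5.8 is 70/12, the load before inflation. With 104 analysed patients it implies 104 / 5.8 = 17.9 clinicians.

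**Per-visit comparison without a clinician term.** With nb bCBT and ne EUC patients analysed and DEFF the design effect above,

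- R = true variance / assumed variance = (DEFF/nb + 1/ne) / (1/nb + 1/ne)
- actual two-sided error = 2 × [1 − Φ(1.96/√R)]

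For 104 v 70 and DEFF 1.48: R = (0.01423 + 0.01429) / (0.00962 + 0.01429) = 1.193 and √R = 1.092. The error is 7.28%, so a 95% interval covers about 92.7%. A simulation with 18 clinicians gave 7.3%.

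| ICC | Analysed | Clinicians | Patients per clinician | DEFF | Type I error |
|---|---|---|---|---|---|
| 0.10 | 104 v 70 | 24 | 4.3 | 1.33 | 6.6% |
| 0.10 | 104 v 70 | about 18 | 5.8 | 1.48 | 7.3% |
| 0.10 | 104 v 70 | 15 | 6.9 | 1.59 | 7.8% |
| 0.10 | 104 v 70 | 12 | 8.7 | 1.77 | 8.7% |
| 0.10 | 138 v 94 | 12 | 11.5 | 2.05 | 10.1% |
| 0.05 | 104 v 70 | about 18 | 5.8 | 1.24 | 6.1% |
| 0.05 | 104 v 70 | 12 | 8.7 | 1.38 | 6.8% |
| 0.05 | 138 v 94 | 12 | 11.5 | 1.53 | 7.5% |

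The 0.05 rows show what happens if the real correlation is weaker, for example because some bCBT patients attend no sessions.

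**Other contrasts, by simulation.** These assume a clinician effect constant over time and within-patient correlations that the documents do not give.

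- Time-by-treatment (104 v 70, 12 to 18 clinicians, correlation 0.3 to 0.7): 5.1% to 5.6% if only months 4, 8 and 12 are modelled, because a constant clinician effect cancels between visits. It is 6.3% to 9.9% if baseline is a time point. With the ICC at zero the same tests ran at 4.9%.
- Treatment effect averaged over the three follow-ups (18 clinicians, correlation 0.7 down to 0.1): about 8% to 11%.

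**Adding site as a fixed effect.** In a per-visit simulation with ICC 0.10 and 104 v 70, two sites gave 7.2%, 8.0% and 9.2% with 18, 15 and 12 clinicians. Treating the 16 CBOCs as site gave 7.8% to 8.0% with 16 to 18 clinicians. With the ICC at zero the result was 5.2%.

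**The case against.** The strongest reply is that 7.3% does not describe the test the plan names, which is time-by-treatment. If that test uses follow-up visits only, it is nearly unaffected. This stands as a limit on the figure. But Aim 2 also asks whether the arms differ at post-treatment and at 8 and 12 months, which is a per-visit question, and the plan does not exclude baseline as a time point.

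Second, calling the model mixed leaves the random effects open, so a clinician effect is not excluded. That is true. But no text asks for one, and the same paragraph rules out adjusting for variables not chosen in advance. That rule concerns covariates, yet it makes a later addition harder to defend.

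Third, the closed form leaves out the covariates. Modality is described only for bCBT sessions, so with it in the model the treatment coefficient is not a plain difference of two means. Part of the 0.10 may also be clinic-level correlation shared by both arms. If site means the 16 CBOCs, which the plan does not settle, a site term would remove that part. With one clinician per CBOC, simulation gave 8.0% if all of the correlation is clinician-only, 6.2% if half is shared and 5.7% if three-quarters is. The split is an assumption. This lowers the size but does not bring it to 5%.

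Fourth, 5.8 per clinician belongs to 70 patients and is applied here to 104. This is so, but the 12 to 15 clinicians anticipated in Section 5.1 make the error larger.

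**Conclusion.** The concern holds and should be fixed. The sample size rests on arm-specific clinician clustering, and the only Aim 2 model text does not provide for it. On the plan's inputs a per-visit comparison at nominal 5% runs at about 7.3%. The range is 6.6% to 8.7% for 24 down to 12 clinicians with 104 v 70 analysed, and 10.1% at the upper end. At an ICC of 0.05 the error is 6.1% to 7.5%.

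These figures assume that the model is fitted with the listed terms only and that the clinician effect acts only in bCBT. They leave out covariates. The effect on time-by-treatment depends on whether baseline is modelled, which the plan must state.

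**What to change.** Add to the Aim 2 analysis text in Section 5.6:

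1. For PHQ-9, BDI-II, PCS and MCS, a random effect for the clinician to whom the patient was referred at randomisation, applying in the bCBT arm only (a partially nested model), with Kenward-Roger or Satterthwaite degrees of freedom. Using the referred clinician keeps the analysis intention-to-treat and covers patients who never start or who change clinician.
2. For the response outcome, the equivalent logistic mixed model. If it does not converge, which is a real risk with 12 to 15 clinicians, use cluster-robust errors with a small-sample correction.
3. A statement of whether baseline is a time point, and the within-patient covariance structure.
4. A record of whether any EUC patient sees a study clinician, since "Participants in EUC will NOT be restricted from any mental health services", with a sensitivity analysis if this is common.

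The cost is a few sentences and slightly more complex code. The referred clinician is already known for each bCBT patient.

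Intervals will widen. Taking the plan's 70 v 70 as 80% power, the effective bCBT number is 104/1.593 = 65.3 with 15 clinicians and 104/1.767 = 58.9 with 12. Power = Φ(2.80 × √[(2/70)/(1/n + 1/70)] − 1.96), where n is the effective number. This gives about 79% and 76%, before any degrees-of-freedom penalty.

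That calculation applies 0.10 to the repeated-measures-adjusted sample size, as the plan does. If 0.10 is instead a per-visit correlation with a constant clinician effect, the loss is larger. An effect size of 0.30 without repeated measures needs 175 per arm, so 70 implies an unstated within-patient correlation of about 0.10 over three visits. The visit mean then has variance (1 + 2 × 0.10)/3 = 0.40, its clinician ICC is 0.10/0.40 = 0.25, and power is about 68% with 15 clinicians and 63% with 12. The plan should say which reading it intends.
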